## 9.4 Key Elements of Analysis Plan

The primary comparison of interest will be the treatment difference over 6 months between DHA-PQP plus TQ and DHA-PQP alone using a Logrank test. Point estimates will be derived from Kaplan Meier methods and include all subjects in the ITT population. Subjects who were lost to follow up or did not relapse by the end of the follow up will be censored at the time of withdrawal or completion of the study.

Note that data from the Day 195 visit will be not used in the assessment of relapse at 6 months. The last data to be used is the data from the Day 180 visit.

Subjects will be considered to have demonstrated relapse-free efficacy at six months if **all** of the following are true:

- Subject had a non-zero *P. vivax* asexual parasite assessment on Day 1. (Subjects who do not meet this criteria will be censored, with time to relapse censored at 0 days).
- Subject demonstrated initial clearance of *P. vivax* parasitemia. (Subjects who do not meet this criteria will be considered to have relapsed with time to relapse = 0 days).
- Subject had a non-zero *P. vivax* asexual parasite assessment on Day 1. (Subjects who do not meet this criteria will be censored, with time to relapse censored at 0 days)
- Subject demonstrated initial clearance of *P. vivax* parasitaemia. (Subjects who do not meet this criteria will be considered to have relapsed with time to relapse = 0 days)
- Subject has no positive asexual *P. vivax* parasite count at any assessment prior to the scheduled Day 180 visit following initial parasite clearance. (Subjects who do have a positive count will be considered to have relapsed with time to relapse = (date of first positive count) – (date of Day 1 visit) days).
- Subject did not take a concomitant medication with anti-malarial activity (excluding study treatment) at any point between day 1 and the scheduled Day 180 visit. (Subjects who did take a drug with anti-malarial activity but never had a positive asexual *P. vivax* parasite count after initial clearance will be censored, with time to relapse censored at (date of medication start) – (date of Day 1 visit) days).
- Subject has a scheduled Day 180 assessment, and is parasite free at this time point. (Subjects who do not have a Day 180 visit and have not already failed or been censored will be censored at (date of final parasite assessment) – (date of Day 1 visit) days).

All statistical testing will be performed using a significance level of 0.05.

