
Summary of the proportion of participants with relapse-free efficacy at six months by treatment group as n (%), including the sub-reasons for why participants are not considered relapse-free defined in Section 11.6.3 (Table 2.5). Note, only the sub-reasons that apply to the population being displayed will be included.
 
Analysis table (Table 2.8) will show:
 
 Number of participants with an observed relapse and numbers of participants censored (censored prior to 6 months, and censored relapse-free at 6 months) Estimates for time to relapse: 1st quartile, median, 3rd quartile and associated 95% confidence intervals Kaplan-Meier estimate and 95% confidence interval of the relapse-free efficacy rate at 6 months for each treatment Hazard ratio of TQ+DHA-PQP vs DHA-PQP only over the first 6 months and associated 95% CI and p-value from Cox's proportional hazards analysis. Hazard ratio of TQ+DHA-PQP vs PQ+DHA-PQP (secondary endpoint) over the first 6 months and associated 95% CI. Hazard ratio of PQ+DHA-PQP vs DHA-PQP only (secondary endpoint) over the first 6 months and associated 95% CI. Kaplan-Meier survival curves will also be produced (Figure 2.1).
Subgroup Analyses
If the treatment by battalion interaction is found to be statistically significant in the Cox's

Primary Statistical Analyses
 
Proportional Hazards analysis, the analysis will be conducted separately for each battalion. Similarly, the Kaplan-Meier curves for time to relapse will be produced separately for each battalion.

Sensitivity and Supportive Statistical Analyses

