
By genetic classification of First P. vivax Recurrence
 
Repeat primary analysis censoring participants with homologous infections (Table 2.13) and censoring participants with heterologous infections (Table 2.14), present: Number of participants with an observed relapse and numbers of participants censored

Primary Statistical Analyses
Kaplan-Meier estimate and 95% confidence interval of the relapse-free efficacy rate at 6 months for each treatment. Kaplan-Meier quartile estimates and 95% confidence intervals of time to relapse Kaplan-Meier survival curves will also be produced (Figure 2.3 and Figure 2.4).

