11.5.2. Reporting Standards

General	

The current GSK Integrated Data Standards Library (IDSL) will be applied for reporting, unless otherwise stated (IDSL Standards Location: https://spope.gsk.com/sites/IDSLLibrary/SitePages/Home.aspx):
 
 4.03 to 4.23: General Principles 5.01 to 5.08: Principles Related to Data Listings 6.01 to 6.11: Principles Related to Summary Tables 7.01 to 7.13: Principles Related to Graphics 	
Formats	

GSK IDSL Statistical Principles (5.03 & 6.06.3) for decimal places (DP's) will be adopted for reporting of data based on the raw data collected, unless otherwise stated. Numeric data will be reported at the precision collected on the eCRF. The reported precision from non eCRF sources will follow the IDSL statistical principles but may be adjusted to a clinically interpretable number of DP's, including:
 
 Proportions and their Confidence Intervals will be presented to 3 decimal places. Rates and their 95% Confidence Intervals will be presented to 1 decimal place 	
Planned and Actual Time	

Reporting for tables, figures and formal statistical analyses: Planned time relative to dosing will be used in figures, summaries, statistical analyses and calculation of any derived parameters, unless otherwise stated. The impact of any major deviation from the planned assessment times and/or scheduled visit days on the analyses and interpretation of the results will be assessed as appropriate. Reporting for Data Listings: Planned and actual time relative to study drug dosing will be shown in listings (Refer to IDSL Statistical Principle 5.05.1).
	

Unscheduled or unplanned readings will be presented within the participant’s listings.
	

Unscheduled Visits
	

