11.6. Appendix 6: Derived and Transformed Data

11.6.1. General

Multiple Measurements at One Analysis Time Point
 
If there are multiple assessments within the same window which are not unscheduled visits, the earliest result will be used in the summaries. All values will be listed.
 
For ECGs, if there are multiple assessments at the same visit, the mean will be derived and used in any derivation of summary statistics but if listed, all data will be presented.
 
Participants having both High and Low values for Normal Ranges at any post-baseline visits for safety parameters will be counted in both the High and Low categories of “Any visit post-baseline” row of related summary tables. This will also be applicable to relevant Potential Clinical Importance summary tables.

--

Study Day

Study Day 1 is defined as the day the first dose of DHA-PQP was taken. Study day >1 is calculated as the number of days from the date of the Study Day 1: Ref Date = Missing → Study Day = Missing Ref Date < Date of Study Day 1 → Study Day = Ref Date – Date of Study Day 1 Ref Date ≥ Date of Study Day 1 → Study Day = Ref Date – (Date of Study Day 1) + 1
 
Study Day 180 refers to a time point exactly 179 days after Study Day 1, whereas the ‘Day 180 visit’ refers to the nominal Day 180 assessments which did not necessarily occur on Study Day 180.

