11.6.3. Efficacy**Efficacy endpoints****Relapse free efficacy at six months**

Relapse is defined as any recurrence of *P. vivax* malaria after clearance of the initial infection.

Participants will be considered to have demonstrated relapse-free efficacy at six months if all of the following are true (also described in [Figure 1](#)):

Participant had a non-zero *P. vivax* asexual parasite count at baseline. Participants who do not meet this criterion will be censored, with time to relapse censored at 0 days.

Participant demonstrated initial clearance of *P. vivax* parasitemia. This is defined as two negative asexual *P. vivax* parasite counts, with at least 6 hours between the counts, and no positive counts in the interval. Participants who do not meet this criterion will be censored with time to relapse censored at 0 days.

Participant has no positive asexual *P. vivax* parasite count at any assessment prior to or on Day 180 visit following initial parasite clearance. Participants who do have a positive count will be considered to have relapsed with time to relapse = (date of first positive count) – (date of Study Day 1) days.

Participants did not take a concomitant medication with anti-malarial activity (excluding study treatment) at any point between Study Day 1 and their last parasite assessment. Participants who did take a drug with anti-malarial activity but never had a positive asexual *P. vivax* parasite count after initial clearance will be censored with time to relapse censored at (date of last negative parasite assessment prior to concomitant medication start) – (date of Study Day 1) days. If a participant has not had a negative assessment prior to the concomitant medication start date, they will be censored at 0 days.

[figure not shown]
Efficacy endpoints

Participant is parasite-free at 6 months. This is defined as a negative asexual *P. vivax* parasite count at the first parasite assessment performed on or after Study Day 170.

Participants who do not have a Day 180 visit and have not already failed or been censored will be censored at (date of final parasite assessment) – (date of Study Day 1) days).

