Participant is parasite-free at 4 months. This is defined as a negative asexual *P. vivax* parasite count at the first parasite assessment performed on or after Study Day 105 (up to and including Study Day 135).

Participants who do not have a Day 120 visit and have not already failed or been censored will be censored at (date of final parasite assessment prior to Day 120) – (date of Study Day 1) days.

If a participant has a relapse outcome and a censored outcome, they will be considered to be a relapse, even if the time point of the relapse is later than the time point of censoring. For example, a participant who took a medication with anti-malarial activity at Study Day 32, but remained parasite-free after initial clearance until Study Day 68 will be treated as a relapse at Study Day 68.

Figure 2 Flowchart of algorithm for relapse-free efficacy at 4 months

Efficacy endpoints
Relapse free efficacy at 6 months missing=failure definition

In addition to those with a positive asexual P. vivax parasite count at any assessment prior to or on Study Day 190, the following participants will also be defined to have relapsed:
 
Participant did not demonstrate initial clearance of P. vivax parasitaemia (i.e. did not have two negative asexual P. vivax parasite counts, with at least 6 hours between the counts, and no positive counts in the interval)
 
Participant took a concomitant medication with anti-malarial activity at any point between Study Day 1 and their last parasite assessment. A list of all concomitant medications will be reviewed by a GSK clinician prior to unblinding the study, and classified accordingly.
 
Participant does not have a parasite assessment between Study Day 170 and 190.
 
Participants with a zero P. vivax asexual parasite count at baseline will be excluded from the analysis.

Genetic classification of relapse (heterologous/homologous)

Relapse-free efficacy at 6 months will be assessed separately according to whether the first P. vivax re-infection is homologous or heterologous to the original infection. The definition is as detailed above but heterologous infections will be censored at the time at which they occur for the endpoint looking at homologous infections only; and homologous infections will be censored at the time at which they occur for the endpoint looking at heterologous infections only.

Recrudescence

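### Does the unstated reading day of the 6-month Kaplan-Meier rate distort the headline relapse-free rates?

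*SAP*

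**What the plan says.** Table 2.8 is a headline display. Its contents, listed in SAP 7.1.5.1, include the "Kaplan-Meier estimate and 95% confidence interval of the relapse-free efficacy rate at 6 months for each treatment". The mock shell TTE1 repeats the label, and its footnote gives only the method. Neither gives a day.

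The definitions around that rate are these:

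- **Relapse.** SAP 11.6.3 looks for a positive asexual "parasite count at any assessment prior to or on Day 180 visit following initial parasite clearance". A participant with one "will be considered to have relapsed with time to relapse = (date of first positive count" minus the date of Study Day 1).
- **Visit window.** Protocol 7.1 and SAP 11.3.1 allow the Day 180 visit on Study Days 170 to 190. The missing=failure rule in SAP 11.6.3 uses the same window: "Participant does not have a parasite assessment between Study Day 170 and 190".
- **Day versus visit.** SAP 11.6.1 separates the two: "Study Day 180 refers to a time point exactly 179 days after Study Day 1", while the visit need not fall on that day.
- **Completers.** Protocol 9.4 says that those who "did not relapse by the end of the follow up will be censored at the time of withdrawal or completion of the study". The readable text of SAP 11.6.3 gives no separate date for them. The Figure 1 flowchart is not shown.
- **Time convention.** SAP 11.5.2 sets a default: "Planned time relative to dosing will be used in figures, summaries, statistical analyses and calculation of any derived parameters, unless otherwise stated".

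The summary measure in SAP 7.1.2 is the hazard ratio over six months, not the Kaplan-Meier rate.

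**The concern.** Take a relapse first found at a Day 180 visit held on Study Day 185. It enters the Table 2.8 row counting relapses up to and at six months. Its event time is 184 days, so a curve read at Study Day 180 (t = 179) has not yet dropped for it. One table could then print a relapse count and a relapse-free rate that do not match.

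Reading later is no clean escape. Relapse-free completers are censored at their own visits from Day 170 on, so the risk set shrinks and one late relapse produces a large step down.

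At stake would be the absolute rates and their intervals in Table 2.8, any number needed to treat derived from them, and the same rate in Table 2.10 and in the genetic analyses ("Repeat primary analysis censoring participants with homologous infections (Table 2.13) and censoring participants with heterologous infections (Table 2.14").

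**Working it through.** **Planning figures (Protocol 9.2.1).** Relapse-free rates are 50% on DHA-PQP alone and 85% on each active arm, with 50 per arm and 10% withdrawal.

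- Expected relapses: 50 × (0.50 + 0.15 + 0.15) = 40, and 40/150 = 26.7%, as stated.
- Implied hazard ratio: ln 0.85 / ln 0.50 = 0.234. With 45 per arm, expected events are 45 × (0.50 + 0.15) = 29.25. Power is 0.975 (Schoenfeld), 0.918 (Freedman) or 0.956 (two proportions). All exceed the stated 90%.

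The documents give no figure for the Kaplan-Meier reading itself.

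**Mechanism.** S(t) is the product over event times u ≤ t of (1 − d_u/n_u). Take 50 controls with 25 relapses, no dropout, negative final visits spread over Days 171 to 189, and k relapses first found after Day 180. At Study Day 180, S = 1 − (25 − k)/50.

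| k | Read at Study Day 180 | Read at end of curve | Crude |
|---|---|---|---|
| 0 | 50% | 50% | 50% |
| 1 | 52% | 46.8% | 50% |
| 2 | 54% | 42.1% | 50% |
| 3 | 56% | 35.9% | 50% |

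For k = 1, the late relapse on Day 183 meets 10 at risk: 0.52 × 9/10 = 0.468. With 7 relapses in 50 on tafenoquine and 0, 1 or 2 found late, the Day 180 reading is 86%, 88% or 90%, and the end-of-curve reading is 86%, 82.8% or 72.9%.

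**Expected size.** Simulation with 2,000 replicates per setting. Assumptions not given in the documents: constant hazard after Day 28, half of relapses found at unscheduled visits, final visit uniform on Days 170 to 190, no dropout.

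| | Tafenoquine | DHA-PQP alone |
|---|---|---|
| Observed relapse-free | 84.9% | 49.8% |
| Read at Study Day 180 | 85.4% | 51.3% |
| Shift (from unrounded values) | +0.5 | +1.4 |
| SD of the estimate | 5.1 | 7.3 |
| Shift / SD | 0.10 | 0.19 |
| Relapses left out per arm | 0.4 | 1.2 |
| Shift, 0% to 80% unscheduled | +1.1 to +0.2 | +2.9 to +0.6 |
| Shift, visits within ±2 days | +0.3 | +1.0 |
| Mean, end-of-window reading | 80.6% | 39.8% |

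The SDs agree with simple binomial errors: √(0.85 × 0.15/50) = 5.0 points and √(0.5 × 0.5/50) = 7.1 points. The 95% half-widths are thus about 1.96 × 5.05 = 9.9 and 1.96 × 7.07 = 13.9 points.

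**Effect on the comparison.**

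- Difference in rates: 84.9 − 49.8 = 35.1 points observed; 85.4 − 51.3 = 34.1 at Study Day 180.
- Number needed to treat, taken as the reciprocal of the difference: 1/0.351 = 2.85 and 1/0.341 = 2.93. Both round to 3.
- Cox model: it uses all event times, so the reading day does not enter. Even moving final-window dates to the nominal day changes the median hazard ratio only from 0.230 to 0.229.

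**Is agreement with the printed count the right test?** With 10% dropout spread over follow-up (control arm, half of relapses found at unscheduled visits), the not-relapsed proportion is 53.1% and the Kaplan-Meier rate at Day 180 is 51.3%. Placing all Day 170 to 190 outcomes on Day 180 gives 50.0%. That is closer to the true 50%, but the gap from the count grows from 1.8 to 3.1 points. Under censoring the two quantities differ by design.

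**The case for a change.** The case for a change is that this is a headline estimate, that several readings can be defended, and that fixing the day before unblinding costs one line. A reading at t = 180 on the date-difference scale is Study Day 181, and nothing expressly rules out the end of the curve. With unscheduled detection from 80% down to 0%, the end-of-curve and Day 180 readings differ by about 5 to 17 points on DHA-PQP alone and 2 to 8 on tafenoquine. In the base case at least one relapse is left out of a Day 180 reading in 69% of control arms and 36% of tafenoquine arms. The planned-time default does not settle it, because SAP 11.6.3 states otherwise by using dates. Were it applied to completers only, the shifts would grow to +0.9 and +2.4 points.

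What stands is that the day is unwritten in the text that can be read, and that the rate and the count in Table 2.8 need not match. The rest does not carry a change:

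- The large figures belong to the end-of-curve reading. A rate at six months is ordinarily read at the six-month day, and SAP 11.6.1 defines Study Day 180.
- Some of the relapses left out belong outside a Day 180 rate: about 0.28 of 1.2 per control arm began after Day 180.
- No relapse is hidden. Tables 2.5, 2.11 and 2.12 and the count row of Table 2.8 include relapses up to the visit.
- Moving all Day 170 to 190 outcomes to Day 180 has its own costs. It departs from the explicit date formula and shifts relapses known to fall on Days 170 to 179. If done for the curves only, they would use different times from the Cox model whose proportional hazards they are meant to check.

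**Conclusion.** No change follows. The SAP leaves a reading day unwritten, and an analyst would fill that gap with Study Day 180. On that reading the rates rise by about 0.5 points (tafenoquine) and 1.4 points (DHA-PQP alone), with ranges of 0.2 to 1.1 and 0.6 to 2.9 as unscheduled detection goes from 80% to 0%. In the base case the shifts are 0.1 to 0.2 of a standard deviation, the arm difference is understated by about 1 point, and the primary hazard ratio and p-value are not materially affected.

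These sizes rest on assumed visit timing and detection, which the documents do not give. The on-site clinic, open at all hours (Protocol 4.1), makes the high-detection end of the range plausible. The 4-month rate in Table 2.16 has a similar form; no size was worked out for it.

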7.2. Secondary Efficacy Analyses

7.2.1. Endpoints / Variables

Relapse-free efficacy four months post-dosing
Time to relapse
Time to fever clearance
Time to asexual parasite clearance
Time to gametocyte clearance
Percentage of Participants with Recrudescence

7.2.2. Summary Measures

The summary measure for all time to event endpoints will be hazard ratios. For the percentage of participants with recrudescence the treatment difference will be calculated.

7.2.3. Population of Interest

The secondary efficacy analyses will be based on the microbiologic-Intent-To-Treat population.

7.2.4. Strategy for Intercurrent (Post-Randomization) Events

The treatment effect to be estimated will be the hypothetical effect if all participants had stayed on their randomised medication.

The time to the first event of interest (i.e. *P. vivax* relapse, fever clearance, asexual parasite clearance or gametocyte clearance) will be used in the analysis.

Participants who discontinue treatment will be included in the analysis and handled the same as participants who remain on treatment as described in Section 11.6.3.

7.2.5. Statistical Analyses / Methods

Details of the planned displays are provided in [Appendix 11: List of Data Displays](#). The format of data displays will be based on GSK data standards and statistical principles.

7.2.5.1. Statistical Methodology Specification

Secondary Statistical Analyses
Endpoints / Variables
Relapse-free efficacy at 4 months

Secondary Statistical Analyses

Time to relapse Time to fever clearance Time to asexual parasite clearance Time to gametocyte clearance

Model Specification

mITT population Estimates for time to endpoint will be determined for each treatment group using Kaplan-Meier methods. Cox's proportional hazards analysis, including terms for battalion and treatment for calculation of Hazard Ratios for time to fever clearance, time to asexual parasite clearance, time to gametocyte clearance, and relapse-free efficacy at 4 months.

Model Checking & Diagnostics

The proportional hazards assumption should be assessed including a check of the Kaplan-Meier curves. The shape of the curves should be similar for the treatment groups with the separation between the curves remaining proportional across time. A complementary log-log plot may also be used to check the proportional hazards assumption. If the proportional hazards assumption is violated a logistic regression model will be performed instead using a binary response variable of event vs no event (e.g. fever clearance vs no fever clearance) and including battalion and treatment as covariates.

Model Results Presentation

Time to relapse is covered in Table 2.8. Tables 2.16 to Table 2.19: Number of participants with the endpoint and number censored Estimates for time to the endpoint: 1st quartile, median, 3rd quartile and associated 95% confidence intervals For the relapse-free efficacy at 4 months endpoint only, the Kaplan-Meier estimate and 95% confidence interval of the relapse-free efficacy rate for each treatment at 4 months. For time to parasite clearance, time to fever clearance and relapse-free efficacy at 4 months: Hazard ratio (TQ+DHA-PQP vs DHA-PQP only, TQ+DHA-PQP vs PQ+DHA-PQP and PQ+DHA-PQP vs DHA-PQP only) and 95% confidence interval. Kaplan-Meier survival curves will be produced for time to fever clearance (Figure 2.5), time to asexual parasite clearance (Figure 2.6), and time to gametocyte clearance (Figure 2.7).

Subgroup Analyses

No subgroup analyses are planned for time to fever clearance, time to asexual parasite clearance, or time to gametocyte clearance. For relapse-free efficacy at 4 months, if the treatment by battalion interaction is found to be statistically significant in the analysis of the primary endpoint (relapse-free efficacy at 6 months), the analysis will be conducted separately for each battalion.

Sensitivity and Supportive Analyses

No sensitivity analyses are planned for these endpoints.

Secondary Statistical Analyses
Endpoint / Variable

Percentage of Participants with Recrudescence - see Section 11.6.3 for derivations including censoring

Secondary Statistical Analyses
Model Specification
Descriptive statistics only 95% Wilsons confidence intervals for percentage of participants with recrudescence in each treatment group, and the treatment difference in the percentages with 95% Newcombe confidence intervals (TQ+DHA-PQP vs DHA-PQP only, TQ+DHA-PQP vs PQ+DHA-PQP and PQ+DHA-PQP vs DHA-PQP only). mITT population
Model Checking & Diagnostics
Only summary statistics are planned for this endpoint therefore no model checking is required.
Model Results Presentation
Summary table showing the number of participants with recrudescence or censored, percentage of participants with recrudescence and 95% CI for each treatment group, plus treatment difference and 95% CI (Table 2.20).
Subgroup Analyses
No subgroup analyses are planned for this endpoint.
Sensitivity and Supportive Analyses
No sensitivity analyses are planned for this endpoint.

